9.1. Primary Assessment

9.1.1. Overall morphine (equivalents) consumption for each patient during hospitalization

9.1.2. Absolute pain scores and pain relief scores

9.2. Secondary Assessments

9.2.1. Methadone clearance

9.2.2. Maximum plasma methadone concentration

9.2.3. Area under the curve (AUC) of plasma EDDP vs time

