Study Design	Randomized, controlled, modified, Dixon up and down dose-finding design (1). Patients receive standard monitoring for anesthesia and postoperative care. Surgical and anesthesia (except for opioid use) care are not altered for study purposes. All patients are induced by propofol and muscle relaxants. In the first cohort, subjects are randomized 1:2 to either control (standard intraop opioid at anesthesiologists' discretion) or methadone HCl (0.4 mg/kg ideal body weight, IBW). Based on an interim analysis for the initial treatment dose (0.4mg/kg), the second cohort will be randomized 1:2 to either control (standard intraop opioid) or methadone HCl (0.3 mg/kg ideal body weight, IBW). Subjects in the study groups will receive methadone (IV bolus, after induction of anesthesia) as their primary intraoperative opioid, rather than leaving the choice of intraoperative opioid to the anesthesiologist. Intraoperative breakthrough pain will be treated at the discretion of the anesthesiologist with fentanyl. In the control groups, intraoperative opioid administration will be left at the discretion of the anesthesia providers. Patient controlled analgesia as prescribed by the clinical team, using hydromorphone or morphine, will be used to treat postoperative pain relief.
Inclusion and Exclusion Criteria	Inclusion Criteria 1. Age 11-18 years 2. Undergoing general anesthesia and idiopathic posterior spinal fusion surgery with anticipated postop inpatient stay of > 3 days 3. Signed, written, informed consent from legal guardians and assent from patient Exclusion Criteria 1. History of liver or kidney disease. 2. Females who are pregnant or nursing. 3. Developmental delay and/or neuromuscular scoliosis
Measurements	Total intraoperative and postoperative care unit (PACU) opioid administration will be recorded from the patient's medical record. Daily opioid consumption will be calculated from the PCA utilization and electronic medical records (EMRs) for up to 6 postoperative days. Pain intensity will be assessed using the Wong-Baker FACES scale. Pain relief is also assessed using a Colored-Visual Analog Scale. Blood and urine samples will be collected for 96 hrs after methadone dosing for determination of methadone and metabolite concentrations by HPLC-mass spectrometry. Subjects will be genotyped for major polymorphisms of the methadone metabolizing enzyme CYP2B6.

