Statistical Methodology	Demographics data including race, sex, and age will be analyzed. Baseline characteristics of the cohort will be described. Results will be expressed as the mean and standard deviation.
Outcomes	Primary: Intraoperative, postoperative and daily cumulative opioid utilization Secondary: Methadone and metabolite enantiomers plasma AUC, maximum concentration, metabolite /methadone AUC ratios, metabolite formation clearance correlation of methadone enantiomer clearances and metabolite formation clearances, influence of CYP2B6*6 hetero or homozygote genotype

on above primary and secondary outcomes

1. Specific Aims.

- 1.1. To study the effects of a single dose of methadone on postoperative pain and opioid consumption in pediatric surgical patients.
- 1.2. Determine the pharmacokinetics of IV methadone (0.3-0.5 mg/kg) in children
- 1.3. Determine cytochrome P4502B6 (CYP2B6) genotype in patients receiving methadone, and any relationship to methadone clearance.
- 1.4. Determine from the primary caregiver the influence of the environment, social and psychological, on post-operative pain.

2. Background

Inadequate pain relief has a significant psychological impact upon children, including alterations in their perceptions of future painful experiences and medical procedures (1). The psychological ramifications of pediatric pain include posttraumatic stress disorder, lack of adherence to treatment, poor coping skills, changes in accuracy in the self-report of pain, and lack of trust in health-care providers (2). The degree to which this pain is controlled impacts the ability of patients to cope with the next pain episode. Patients undergoing major spine surgery experience severe pain in the postoperative period, which may increase morbidity and the incidence of complications, as well as prolong postoperative rehabilitation. Postoperative pain itself is a risk factor for development of chronic pain syndromes(3,4).

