Evaluating the role of methadone in pediatric spinal surgery patients is advantageous because 1) high dose of opioids are routinely used during and after the surgery, 2) methadone is one of the commonly used opioids for this surgery, 3) an arterial catheter or a second IV catheter is needed for the surgery and can be used to draw blood samples, 4) prolonged analgesia from methadone is expected to decrease the need for additional opioids.

Assessment of pain has become standard practice in the treatment of pediatric patients. Several pain scales including the Wong-Baker FACES scale, the Oucher Scale and the Visual Analog Scale (VAS) have been USED in children who were experiencing pain (14,15).

In this study, we propose to evaluate postoperative opioid consumption, pain intensity and pain relief in pediatric patients undergoing posterior spinal fusion who will receive a single dose of methadone during surgery. In addition, we will study dose effect of ing various doses of methadone, between 0.3 – 0.5mg/kg IBW. Secondarily, we will determine the pharmacokinetics of higher doses of IV methadone in children who are undergoing anesthesia and surgery. Lastly, we will determine the role of CYP2B6 genotype on methadone pharmacokinetics.

3. Drug Information

Methadone hydrochloride is a synthetic μ -agonist with multiple actions qualitatively similar to those of morphine. Onset of effect is about 2-10 min for parenteral dosing. Methadone is primarily metabolized by N-demethylation to an inactive metabolite, 2-ethylidene-1,5-dimethyl-3,3-diphenylpyrrolidene (EDDP). In vitro, cytochrome P450 enzymes, primarily CYP3A4 and CYP2B6 are responsible for conversion of methadone to EDDP and other inactive metabolites. In vivo, CYP2B6 is a major determinant of metabolism to inactive metabolites which are excreted mainly in the urine. The terminal half-life ($T_{1/2}$) in healthy children averages 24-36 hrs. Like adults, in teenage children, most common side effect of methadone, like other opioids, is sedation, nausea and vomiting. Respiratory depression is the chief hazard associated with methadone, like all opioids. QT prolongation and serious arrhythmia have been observed during treatment with methadone and have been associated with doses

>200 mg/day(16).

4. Eligibility

4.1. Inclusion Criteria.

- 4.1.1. Age 11-18 years
- 4.1.2. Undergoing general anesthesia and idiopathic posterior spinal surgery with anticipated postop inpatient stay of > 3 days

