9.2.4. Maximum plasma EDDP concentration

9.2.5. AUC (plasma EDDP)/AUC (plasma methadone)

9.2.6. Cmax (plasma EDDP)/Cmax (plasma methadone)

9.2.7. Urine concentration of methadone and EDDP

9.2.8. Side effects of opioids

9.3. Analysis.

9.3.1. Sample Size- we decided to use our pilot study data which looked into the pharmacokinetics of methadone in pediatric surgical patients attending St. Louis Children Hospital. This is actually the pooling place for the present study and therefore the information provided is a "true" sample of the data to be collected. The pilot study revealed that patients undergoing spinal fusion surgery used an average of 274 mg of morphine equivalents within 72 hours post-surgery with a standard deviation of 82 mg. Based on this information and assuming a 2-sided test of two independent sample means with α 0.05, we were able to estimate that the proposed study will have at least 80% power to detect 30% decrease in the total postoperative consumption of morphine or morphine equivalents among the patients assigned to the two treatment groups combined when compared to the control group

patients. Specifically, with a total sample of approx. 60 patients assigned equally across study groups (1:2 randomization), we will have adequate statistical power to detect a clinically meaningful reduction of opioid use in patients receiving a single dose of methadone before incision.

To study the effect size between two groups, power calculations were made with alternative mean differences in morphine consumption over 72 hours post-surgery with assumed variation range and a 2-sided test with $\alpha = 0.05$. Based on our conservative assumptions, we found that, with a sample as small as 20 in each group, we will have 80% power to detect a minimum difference between 10 and 20 mg of morphine use, depending on the observed variability between the two groups.

9.3.2. Statistical Analysis- Baseline characteristics of the cohort will be described. Demographics data including race, sex, and age at study entry will be analyzed using chi-square and t- test appropriate. Total daily opioid consumption and pain scores using both Wong-Baker FACES and colored visual analogue scale, will be compared between the groups. Outcome measures will be expressed by the mean and standard deviation. Group outcomes will be compared across the two or three groups, using t-test and/or analysis of variance, ANOVA and MANCOVA to account for potential cofounders.

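### The Synopsis and section 9.1 name different primary outcomes, neither is the 72-hour opioid total that appears to underlie the power statement, and no rule says how several primaries decide the trial.

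*Combined protocol and SAP*

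**What the plan says.** Two places in the combined protocol and SAP name primary outcomes.

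- **Synopsis, Outcomes row:** "Primary: Intraoperative, postoperative and daily cumulative opioid utilization". Pain is in neither the primary nor the secondary list of that row, although the Synopsis Objective and Specific Aim 1.1 both include postoperative pain.
- **Section 9.1:** "Overall morphine (equivalents) consumption for each patient during hospitalization" (9.1.1) and "Absolute pain scores and pain relief scores" (9.1.2). No scale, time point or summary measure is attached to the pain items.

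The sample-size text in 9.3.1 uses a pilot in which spinal fusion patients "used an average of 274 mg of morphine equivalents within 72 hours post-surgery with a standard deviation of 82 mg". It claims at least 80% power, two-sided alpha 0.05, for a 30% fall in total postoperative consumption "among the patients assigned to the two treatment groups combined when compared to the control group". Its second paragraph again refers to 72 hours after surgery.

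Section 9.3.2 compares total daily opioid use and two pain scales: "Group outcomes will be compared across the two or three groups, using t-test and/or analysis of variance", with MANCOVA also listed.

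Two further passages bear on the time window. Eligibility requires an "anticipated postop inpatient stay of > 3 days", and the Synopsis Measurements row says "Daily opioid consumption will be calculated from the PCA utilization and electronic medical records (EMRs) for up to 6 postoperative days".

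**The concern.** The outcome that decides the trial should be the same wherever it is named, and it should be the one for which power is stated. Here the lists and the power text differ in three ways.

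- **Window.** With an expected stay beyond three days, the 9.1.1 total will normally run past 72 hours and will vary with length of stay.
- **Content.** The Synopsis counts intraoperative opioid as primary, and 9.1.1 does not exclude it. Intraoperative opioid is what randomisation assigns, so including it would put the study treatment into the measure of its own effect.
- **Pain.** It is primary in 9.1 and absent from the Synopsis Outcomes row.

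In addition, 9.3.2 does not carry the powered contrast into the analysis, and no rule governs success when there are several primaries. Two analysts following the document could choose different outcomes, groupings and tests, and reach different conclusions from the same data.

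**Working it through.** **Inputs (9.3.1).** Mean 274 mg, SD 82 mg, 30% reduction, two-sided alpha 0.05, about 60 patients randomised 1:2, read as 20 control and 40 methadone.

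**Which outcome is powered?** The power sentence speaks of total postoperative consumption without repeating a window. Its only mean and SD are 72-hour values, and the next paragraph says 72 hours. That the powered outcome is the 72-hour total is therefore an inference, but a reasonable one.

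**Reproducing the plan's figure.** Difference = 0.30 × 274 = 82.2 mg. For a two-sample t-test, the noncentrality is difference / (SD × √(1/n₁ + 1/n₂)).

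| Comparison | n₁ vs n₂ | Alpha | Noncentrality | Critical t | Power |
|---|---|---|---|---|---|
| Combined methadone vs control | 20 vs 40 | 0.05 | 82.2/(82 × 0.2739) = 3.66 | 2.002 | 94.9% |
| One dose vs control, controls pooled across cohorts | 20 vs 20 | 0.05 | 82.2/(82 × 0.3162) = 3.17 | 2.024 | 87.1% |
| One dose vs concurrent controls only | 10 vs 20 | 0.05 | 82.2/(82 × 0.3873) = 2.59 | 2.048 | 70.5% |
| Combined vs control, Bonferroni over three | 20 vs 40 | 0.0167 | 3.66 | 2.465 | 88.0% |

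The first row confirms the claim of at least 80%. The second and third assume two equal cohorts. The plan randomises 1:2 within each cohort and does not say whether controls are pooled.

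**Does the figure carry over to another window?** For a 30% reduction, power depends only on SD/mean. The pilot ratio is 82/274 = 29.9%. At 20 vs 40, power reaches exactly 80% at an SD of 105.4 mg for the same mean, a ratio of 105.4/274 = 38.5%. A total whose ratio exceeds about 38% would fall below 80%. The documents give no mean or SD for the whole-stay total, for a total that includes intraoperative opioid, or for pain, so power for those outcomes cannot be derived.

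**Effect of having no success rule.** If each primary were tested at 0.05 and any one success counted:

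- two independent tests: 1 − 0.95² = 9.75% (upper bound 2 × 0.05 = 10%);
- three independent tests (opioid, pain, pain relief): 1 − 0.95³ = 14.3% (upper bound 3 × 0.05 = 15%).

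Testing each pain scale or each day separately would raise these further. If all had to succeed, error would not be inflated, but joint power could not be computed without a pain difference and SD.

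**The case against.** The best defence is that this is a small single-centre dose-finding study, that the opioid outcomes overlap, and that daily records should allow a 72-hour total to be derived. The stated power is also conservative. All of that is fair. But several windows can be derived from the same records, and being derivable does not make one of them prespecified. Spare power on one outcome does not limit the choice among outcomes.

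Four stronger readings are tempting, and the documents do not support them.

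- *The trial is underpowered, or its sample size is wrong.* Nothing shows this. Power for the 72-hour total is about 15 points above the claim, and for the whole-stay total it is unknown, not low.
- *No contrast was ever fixed.* Section 9.3.1 states the powered contrast. The fault is that 9.3.2 does not repeat it. The mention of two or three groups may only reflect the optional further cohorts in 6.1.
- *The Synopsis drops pain from the trial's purpose.* Its Objective includes pain; only the Outcomes row leaves it out.
- *The trial has a 14% false-positive rate.* That figure needs three tests and an any-success rule. The plan states neither.

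**Conclusion.** The inconsistency stands and should be resolved before analysis. The two primary lists differ from each other, and neither names the outcome whose mean and SD support the power statement. The claim of at least 80% power is correct for the 72-hour total (94.9%), on the inference that this is the powered outcome and on the assumption that the pilot SD/mean still holds. The second condition is not assured, because the rationale for Amendment 3 says that postoperative pain management in this population has changed since the group's last project. For the primaries as worded in 9.1, power is not derivable from the documents. Error control is undefined: familywise error lies between no inflation (all must succeed) and 14.3% for three independent tests where any success counts (upper bound 15%), with more if scales or days are tested separately.

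**What to change.** Use the same text in the Synopsis, 9.1 and 9.3.

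1. **Opioid primary.** Name one: total postoperative morphine equivalents to 72 hours after surgery, with the same start point as the pilot figure, excluding intraoperative opioids including study methadone. State whether PACU opioid counts and how discharge before 72 hours is handled.
2. **Test.** Combined methadone groups against control, one named test, two-sided 0.05, with that contrast carried into 9.3.2.
3. **Secondary outcomes.** Whole-stay total, intraoperative use, and each dose against control, stating whether controls are pooled across cohorts.
4. **Pain and pain relief.** Fix one scale, time point and summary measure for each. Then apply one rule in both the Synopsis and 9.1: either fixed-order testing after the opioid primary, or co-primary status with a stated any-or-all rule.

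Keeping the whole-stay total as primary would also be coherent, but it would need its own mean, SD and power, which the documents do not supply.

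**Cost.** Mainly wording; no patients are added. Opioid totals may need re-extraction to fit the 72-hour window, since 7.2 does not say when each 24-hour period starts. Use after 72 hours is no longer primary. Pain faces a stricter test under fixed-order testing. If alpha is split over three, power for the 72-hour opioid total falls from 94.9% to 88.0%. If all must succeed, the chance of overall success falls by an amount that cannot be computed from the documents.

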9.2.4. Maximum plasma EDDP concentration

9.2.5. AUC (plasma EDDP)/AUC (plasma methadone)

9.2.6. Cmax (plasma EDDP)/Cmax (plasma methadone)

9.2.7. Urine concentration of methadone and EDDP

9.2.8. Side effects of opioids

9.3. Analysis.

9.3.1. Sample Size- we decided to use our pilot study data which looked into the pharmacokinetics of methadone in pediatric surgical patients attending St. Louis Children Hospital. This is actually the pooling place for the present study and therefore the information provided is a "true" sample of the data to be collected. The pilot study revealed that patients undergoing spinal fusion surgery used an average of 274 mg of morphine equivalents within 72 hours post-surgery with a standard deviation of 82 mg. Based on this information and assuming a 2-sided test of two independent sample means with α 0.05, we were able to estimate that the proposed study will have at least 80% power to detect 30% decrease in the total postoperative consumption of morphine or morphine equivalents among the patients assigned to the two treatment groups combined when compared to the control group

patients. Specifically, with a total sample of approx. 60 patients assigned equally across study groups (1:2 randomization), we will have adequate statistical power to detect a clinically meaningful reduction of opioid use in patients receiving a single dose of methadone before incision.

To study the effect size between two groups, power calculations were made with alternative mean differences in morphine consumption over 72 hours post-surgery with assumed variation range and a 2-sided test with $\alpha = 0.05$. Based on our conservative assumptions, we found that, with a sample as small as 20 in each group, we will have 80% power to detect a minimum difference between 10 and 20 mg of morphine use, depending on the observed variability between the two groups.

9.3.2. Statistical Analysis- Baseline characteristics of the cohort will be described. Demographics data including race, sex, and age at study entry will be analyzed using chi-square and t- test appropriate. Total daily opioid consumption and pain scores using both Wong-Baker FACES and colored visual analogue scale, will be compared between the groups. Outcome measures will be expressed by the mean and standard deviation. Group outcomes will be compared across the two or three groups, using t-test and/or analysis of variance, ANOVA and MANCOVA to account for potential cofounders.

9.3.3. Methadone Calculations -Methadone and EDDP plasma concentration-time data will be analyzed by linear and nonlinear regression analysis using noncompartmental or compartment models to determine total area-under-the-curve (AUC), and systemic clearance. Results will also be analyzed using population methods, with age and dose as covariates, to determine linearity of pharmacokinetic parameters and effects of age.

10. Risk Assessment

10.1. *Methadone* The most common clinical effect of opioids such as methadone is mild sedation. Based on prior experience with this opioid and doses, and prior published experience, some subjects might experience mild sedation for about 0.5-1 hr after methadone administration, were they awake. Since patients will be anesthetized during this period, clinical methadone effects are expected to be no different from those of anesthesia and any other opioid administered during anesthesia. We have further attempted to minimize the risk to the patients by following a conservative approach of two step randomization. The most common adverse effect of methadone is nausea and/or vomiting. Patients will have only clear liquids 6 hours before anesthesia, per standard of care. If nausea and/or vomiting occur, they will be treated using the standard of care for all post-anesthesia nausea and vomiting. Respiratory depression is a potential concern with all opioids, but has not been problematic at the doses of methadone that

have been used in similar previous studies. Mild respiratory depression is defined as respiratory rate <8/min in adults and children older than 10, <12–16 in children age 3-10, and <20 in children younger than two. Severe depression will be defined as the administration of naloxone to a patient with respiratory rate < 6/min. If treatment is required, naloxone will be used. Patients in the hospital are routinely periodically monitored by blood pressure and/or pulse oximetry, and receive supplemental oxygen if dictated, according to good clinical practice.

10.2. *Genotyping* – With regard to the determination of CYP2B genotype: 1) CYP2B genes are not associates with any disorder(s), syndrome(s), or adverse condition. 2) Samples will be kept confidentially. They will be coded, with a key to the code linking code numbers to names kept at a separate location, under lock and key. 3) The link to identifiers will be destroyed at the end of the study. 4) We have no evidence to suggest that testing will provide evidence of previously undiagnosed or unrecognized illness, or susceptibility to illness. 5) We will not use samples for any purpose other than to study genes related to the disposition and response to study drugs. 6) Blood samples will not be used to establish permanent cell lines. 7) Data will be stored under lock and key (office, file cabinet) and only the investigators will have access. If data are published, there will be no link to identifiers. Study data will not be revealed to any organization, individuals other than the subjects, or the subjects themselves. 8) We will not enter any genetic study data in subjects' medical records. 9) Studies are not likely to result in findings that meet the National Bioethics Advisory Commission criteria for disclosure. 10) We will not have genetics counseling available to subjects, as they will not be informed of results and there are no known implications with respect to disease. 11) DNA samples will stripped of identifiers and given a separate code numbers unrelated to the subjects' study identification numbers. The code key will be kept by the PI under lock and key.

10.3. *Special Precautions*. Standard of care for all surgical patients includes placement of an IV, pulse oximetry, ECG and blood pressure monitoring.

10.4. *Procedures to Maintain Confidentiality*. Any information that is obtained in connection with research that can be identified with a subject will remain confidential. The consent form, medical information, flow-sheets, and pharmacokinetic and genetic data will be stored under lock and key (office, file cabinet) and only the PI, physician investigators, and research team will have access.. Statisticians involved in the project will have access to de-identified data for the purposes of analysis.

